|---|--------------------------------------|----------------------------|----------------------|----------------------|---------------------|---------------------|-----------------------|---------------------|---------------------|----------------------------------|------------------------------------|----------------------------------|----------------------------------|---------------------|
| | | Day 1 Dosing Visit | Day 2 Telephone Call | Day 8 Telephone Call | Day 15 Clinic Visit | Day 29 Dosing Visit | Day 30 Telephone Call | Day 36 Clinic Visit | Day 43 Clinic Visit | Day 57 Dosing Visit ^k | Day 58 Telephone Call ^k | Day 64 Clinic Visit ^k | Day 71 Clinic Visit ^k | Day 91 Clinic Visit |
| Urinalysis | X | | | | | | | | | | | | | |
| Haematology | X | X | | | X | X | | X | X | X | | X | X | X |
| Biochemistry | X | X | | | X | X | | X | X | X | | X | X | X |
| Liver function tests | X | X | | | X | X | | X | X | X | | X | X | X |
| Troponin T ^{e,f} | X | X | | | X | X | | X | X | X | | X | X | X |
| CRP | X | X | | | X | X | | X | X | X | | X | X | X |
| Serum testosterone | X | | | | | | | | | | | | | |
| Intervention administration | | | | | | | | | | | | | | |
| Enrolment /confirmation that eligibility requirements still met prior to dosing | | X | | | | X | | | | X | | | | |
| VTP-850 dose | | ChAd | | | | MVA | | | | MVA | | | | |
| Post-dose observation | | X | | | | X | | | | X | | | | |
| Other safety assessments | | | | | | | | | | | | | | |
| Symptom-directed physical examination | | X | | | X | X | | | X | X | | | X | X |
| Vital signs | X | X ^g | | | X | X ^g | | | X | X ^g | | | X | X |
| Medical occurrences | X | | | | | | | | | | | | | |
| Adverse events | | ← | → | | | | | | | | | | | |
| Serious adverse events/AESIs ^c | X ^h | ← | → | | | | | | | | | | | |

Optional schedule to be repeated for participants receiving a third dose of MVA-PCAQ after initial PSA response followed by progression. Schedule to be repeated for participants whose 2nd dose of MVA was delayed.¶

| Visit/Call | Screening Period (42 d) ^a | Intervention Period (Days) | | | | | | | | | | | | |

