4.1.1 Phase 1 – Dose/Regimen Finding Phase

Phase 1 will determine the recommended Phase 2 regimen (RP2R; dose level of both ChAdOx1-PCAQ and MVA-PCAQ, and route of administration of MVA-PCAQ) that will be used in Phase 2 and will follow a 3+3 design.

Participants will be dosed according to [Table 1](#) during the Screening and Intervention Periods [Table 5](#). The first 3 participants will be enrolled in Cohort 1. Enrolment of the first 3 participants in each cohort will be staggered by at least 9 days. The medical monitor will review the safety data for the previous participant, at least 7 days after the prime dose and after the first booster dose of VTP-850, before the corresponding dose is administered to the next participant. The safety review will include data from at least 7 days after each ChAdOx1-PCAQ prime dose; at least 7 days after the first booster MVA-PCAQ dose if administered IM; and at least 14 days after the first booster dose of MVA-PCAQ if administered IV. If 1 or more of the 3 participants has a dose limiting toxicity (DLT), 3 additional participants may be enrolled into Cohort 1. If there is no DLT after the first dose of VTP-850 in the first 3 participants, 3 participants will be enrolled into each of Cohorts 2 and 3 concurrently, with the first participants in Cohorts 2 and 3 staggered by at least 9 days to allow for medical review.

If DLT is not seen in more than 1 participant in Cohort 2 after the first dose of VTP-850, then an additional 3 participants will be enrolled into Cohort 2. Safety data for the DLT period following each booster dose will be assessed by the medical monitor prior to the corresponding booster dose being administered to additional participants.

If DLT is not seen after the first dose of VTP-850 in more than 1 participant in Cohort 3, then an additional 3 participants will be enrolled into Cohort 3. Safety data for the DLT period following each booster dose will be assessed by the medical monitor prior to the corresponding booster dose being administered to additional participants.

A total of 6 participants in each of Cohorts 2 and 3 will be dosed with MVA-PCAQ on Day 29 and Day 57. Therefore, participants who withdraw before dosing, before completion of dosing or who have dose delays will be replaced (unless the reason for not completing dosing per protocol is related to a stopping rule criteria being met).

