If the safety of one or more cohorts is acceptable after all participants have been followed through the DLT period after the first booster dose of VTP-850, then a Phase 2 dosing regimen will be selected based on safety data, and recruitment to Phase 2 will be opened.

A Safety Monitoring Committee (SMC) consisting of the Medical Monitor, sponsor physician, a prostate cancer physician not participating in the trial, and at least 2 investigators will review cumulative safety data and decide whether to enrol each cohort in Phase 1 and whether to open enrolment in Phase 2, and will also choose the RP2R. The SMC will evaluate all events that meet the DLT criteria, taking into consideration the outcome and recovery time of each event.

The DLT evaluation period ends 7 days after each IM injection and 14 days after each IV injection of MVA-PCAQ.

A DLT is defined as any of the following toxicities that occur during the DLT evaluation period and are considered related to trial intervention (Grading is per CTCAE Version 5.0):

- Grade 4 or fatal AE
- Grade 3 or greater hematologic AE that does not recover to Grade 1 or baseline Grade within 72 hours
- Grade 3 or greater hepatic and renal dysfunction that does not improve to \leq Grade 2 within 7 days

Grade 3 or greater AE affecting heart, lung or Central Nervous System (CNS) of any duration (including encephalopathy as defined by Immune Effector Cell Encephalopathy [ICE] or Immune Effector Cell -Associated Encephalopathy criteria [ICAN])

- Grade 3 or greater cytokine release syndrome (CRS) that does not improve to \leq Grade 2 within 72 hours
- Grade 3 or greater clinical AE other than heart, lung or CNS toxicity, hepatic or renal dysfunctions, not resolving to <Grade 2 within 72 hours

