sign a statement of informed consent that meets the requirements of 21 CFR 50, local regulations, ICH guidelines, privacy and data protection requirements, where applicable, and the IRB/IEC or trial centre.

- The medical record must include a statement that written informed consent was obtained before the participant was enrolled in the trial and the date the written consent was obtained. The authorised person obtaining the informed consent must also sign the ICF.
- Participants must be reconsented to the most current version of the ICF(s) during their participation in the trial.
- A copy of the ICF(s) must be provided to the participant.

A participant who is rescreened is not required to sign another ICF if the rescreening occurs within 42 days from the previous ICF signature date, or there is a new ICF including updated safety or trial information.

A1.4. DATA PROTECTION

Participants will be assigned a unique identifier by the sponsor. Any participant records or datasets that are transferred to the sponsor will contain the identifier only; participant names or any information which would make the participant identifiable will not be transferred.

The participant must be informed that his personal trial-related data will be used by the sponsor in accordance with local data protection law. The level of disclosure must also be explained to the participant who will be required to give consent for their data to be used as described in the informed consent

The participant must be informed that his medical records may be examined by Clinical Quality Assurance auditors or other authorised personnel appointed by the sponsor, by appropriate IRB/IEC members, and by inspectors from regulatory authorities.

A1.5. SAFETY MONITORING COMMITTEE

Participant safety will be continuously monitored by the SMC.

The SMC, consisting of the sponsor trial physician, the Medical Monitor, a prostate cancer physician not participating in the trial, and at least 2 investigators will be appointed to review the trial data periodically or when needed and make recommendations concerning the continuation, modification or termination of the trial.

- The timings of SMC meetings will be defined in a trial-specific SMC Charter.
- The SMC will make recommendations about:
 - Opening each cohort in Phase 1
 - Choosing the regimen for Phase 2 and opening enrolment in Phase 2

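### After the IM prime the DLT period closes on Day 8, about a week before the first scheduled laboratory sample, so two of the six DLT criteria go unmeasured in it (minor)

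*Protocol*

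**What the plan says.** **DLT period.** Protocol Section 4.1.1: "The DLT evaluation period ends 7 days after each IM injection and 14 days after each IV injection of MVA-PCAQ". The prime is IM in all three cohorts (Section 6.2, Table 5).

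**Laboratory-based criteria.** Two of the six DLT criteria in Section 4.1.1 depend mainly on blood results. One is "Grade 3 or greater hematologic AE that does not recover to Grade 1 or baseline Grade within 72 hours". The other is hepatic or renal dysfunction of Grade 3 or more that has not improved within 7 days. To count, a toxicity must occur inside the evaluation period.

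**Schedule.** Days 2 and 8 in Section 1.3, Table 1, are telephone calls. The haematology row begins "Haematology | X | X | | | X | X": Screening and Day 1, two blanks for Days 2 and 8, then Days 15 and 29. Biochemistry and liver function follow the same pattern. SAP Section 2.7 also goes from Day 1 to Day 15, and SAP Section 5.1.2 treats Day 1 assessments as pre-dose, apart from post-dose vital signs and treatment-emergent AEs.

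**Decision rules.** Section 4.1.1 ties expansion to the first dose: "If DLT is not seen in more than 1 participant in Cohort 2 after the first dose of VTP-850, then an additional 3 participants" are enrolled, with the same rule for Cohort 3. On data required: "The safety review will include data from at least 7 days after each ChAdOx1-PCAQ prime dose". On spacing: "Enrolment of the first 3 participants in each cohort will be staggered by at least 9 days".

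**Oversight.** The SMC "will review cumulative safety data and decide whether to enrol each cohort in Phase 1". Appendix 1 (A1.5) adds: "The timings of SMC meetings will be defined in a trial-specific SMC Charter". That Charter is not among the documents.

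**The concern.** An expansion rule that counts DLTs presumes that each criterion could have been met in the period being counted. After the prime, two of the six cannot be met from scheduled data. For those two, a finding of no DLT may only mean that no blood was due.

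There are two consequences. First, a Grade 3 laboratory abnormality first seen on Day 15 has no scheduled observation that dates it inside a period that ended on Day 8. Read strictly, it adds nothing to the DLT count, whichever participant it occurs in. Second, the text permits an expansion decision when the last counted participant reaches Day 8, before any post-dose laboratory result exists for him.

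What is at stake is the reliability of the post-prime DLT count in a first-in-human product for which the protocol lists routine laboratory testing as a mitigation of unknown toxicity (Section 2.3.1, Table 3).

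**Working it through.** The plan gives no figure to reproduce, so the check is calendar arithmetic from its own timings.

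**Gap after the prime**
- DLT period end = Day 1 + 7 = Day 8.
- First post-dose sample = Day 15 ±2 = Days 13 to 17.
- Gap = 13 − 8 = 5, 15 − 8 = 7 (target), 17 − 8 = 9 days.
- SAP Table 5 prints the protocol window as Days 12 to 16. The gap is then 4 to 8 days, so the conclusion is unchanged.

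**Scheduled samples inside the DLT period, at target visit days**

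| Dose | DLT period | Samples after dose | Inside |
|---|---|---|---|
| Prime, IM | 7 days | 14 days | 0 |
| Boost, IM | 7 days | 7 and 14 days | 1 |
| Boost, IV | 14 days | 7 and 14 days | 2 |

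The mismatch is specific to the prime.

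**Earliest expansion decision, minimum 9-day stagger**
- Prime doses on calendar days 1, 10 and 19.
- The third participant reaches Day 8 on calendar day 19 + 7 = 26.
- Study days of the three on that date: 26, 17 and 8.
- Target samples fall on calendar days 15, 24 and 33, so two participants have been sampled and the third has not.
- A wider stagger does not help the third participant: at 12 days the study days are 32, 20 and 8, and at 16 days they are 40, 24 and 8.
- Waiting for his sample moves the decision from day 26 to days 31 to 35, a delay of 5 to 9 days before turnaround.

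**Evidence from the sister cohort.** Cohorts 2 and 3 receive the same prime, 2.5×10^10 vp IM. Suppose Cohort 2 is dosed on days 1, 10 and 19 and Cohort 3 on days 10, 19 and 28. At Cohort 2's earliest decision (day 26), three full-dose participants have reached their Day 15 target. At Cohort 3's (day 28 + 7 = 35), five of six have.

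**Decisions already taken.** Table 3 of the protocol reports on the first 14 participants treated. With 3 to 6 in Cohort 1, 14 − 6 = 8 to 14 − 3 = 11 were in later cohorts. Subtracting the initial 3 + 3 leaves 2 to 5 who were expansion or replacement participants. Cohort opening is therefore past, and probably at least one expansion. About 25 are planned for Phase 1, so about 25 − 14 = 11 enrolments lay ahead at that count. SAP Section 2.1 says that Phase 2 has not begun, but not whether Phase 1 enrolment is complete.

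**The case against.** The case for leaving the text alone is substantial, and most of it stands.

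- **The expansion rule absorbs much of the gap.** Cohorts 2 and 3 stop only for more than one DLT. One unseen laboratory DLT in the third participant changes the decision only if another participant already has a DLT. The zero-DLT rule governed the opening of Cohorts 2 and 3, which has happened.
- **Day 8 is a minimum.** The SMC weighs cumulative safety data, so it can see Day 15 abnormalities whether or not they are labelled DLTs, and it may wait. Its Charter or the Safety Monitoring Plan (SAP Section 6.7.8) may already require this.
- **Other safeguards work outside the DLT period.** Unscheduled local tests are allowed (Section 8.4.3). Related Grade 4 or 5 events and related SAEs pause the trial (Section 4.1.6). Persistent related events of Grade 3 or more end a participant's dosing (Section 7.1), and Day 15 results precede the Day 29 boost.
- **Prior exposure.** The full prime dose matches the ChAdOx1 dose used in two earlier VTP-800 trials (Section 4.2.1).

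What remains is narrower. None of these provisions requires laboratory results before expansion. A symptom-free abnormality would not prompt a test during a telephone call, and a non-serious Grade 3 laboratory abnormality triggers no pause. The strict-reading problem also applies to all counted participants, not only the last.

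A reader might infer that cohorts were in fact expanded without laboratory data. The documents do not show this: they give minimum intervals, not actual decision dates, and the Charter is unseen.

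**Conclusion.** The mismatch is real and the severity is minor. Two of the six DLT criteria have no scheduled measurement in the post-prime period. The first sample comes 7 days late at target (range 5 to 9). At the earliest expansion decision, one of the three counted participants has no post-dose laboratory result.

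This assumes that the 7-day IM limit covers the prime, which the 7-day data minimum after the prime supports. It also assumes that no Charter provision already requires the Day 15 results. The number of decisions still affected cannot be stated from the documents.

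Three wider readings are tempting but not supported:
- **The boosts share the defect.** At target days each boost has at least one sample inside its period.
- **The Phase 2 regimen choice is compromised.** It waits for the DLT period after the first boost, by which time Day 15 results exist.
- **Replacements are admitted on an unmeasured DLT count.** Sections 4.1.1 and 6.12 attach no DLT count to replacement.

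**What to change.** Add to Section 4.1.1, prospectively and for the laboratory criteria only:

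> For the haematologic and hepatic/renal DLT criteria, the evaluation period after the ChAdOx1-PCAQ prime runs through the scheduled Day 15 laboratory visit; for all other criteria it ends 7 days after the IM injection. A decision to expand a cohort is made only after the Day 15 haematology, biochemistry and liver function results of the first 3 participants in that cohort have been reviewed.

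If the SMC Charter already imposes this wait, the second sentence can simply cite it.

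**Cost.** There is no new visit or procedure. Each remaining expansion decision waits about 5 to 9 days plus turnaround, and up to 7 days more if a Grade 3 or higher value must be followed through the recovery clause. Participants 4 to 6 and replacements gain no extra stagger, and the four other criteria are unchanged.

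**Limits.** Laboratory toxicity that resolves before Day 15 is still missed, and the 9-day spacing between the first three participants still runs ahead of laboratory results. A blood sample at Day 8 would narrow the first limit but would turn a telephone call into a clinic visit. That is an option for the sponsor, not part of this request.

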4.1.2 Phase 2 – Main Phase

Phase 2 of the trial will consist of 2 sequential stages.

In Stage 1 of Phase 2, 19 additional participants will be enrolled at the chosen Phase 2 regimen. If 4 or more of the 25 participants at the RP2R (out of the 19 Phase 2 participants and the 6 Phase 1 participants who received the same dose regimen according to the dosing schedule) have a PSA response, Stage 2 will be opened to enrolment. If 3 or fewer of the 25 participants receiving the RP2R have a PSA response, no further participants will be enrolled. PSA response is defined as $\geq 50\%$ reduction in serum PSA compared to baseline at any time, measured at two consecutive timepoints, at least 2 weeks apart. The decision to open recruitment in Stage 2 will be made by the SMC after reviewing available safety and efficacy data after at least 4 participants have exhibited a PSA response.

4.1.3 Selection of Phase 2 Regimen

This trial will test 2 dose levels of ChAdOx1-PCAQ and 2 dose levels of MVA-PCAQ delivered IM and one dose level of MVA-PCAQ delivered IV.

Based on previous experience with vaccines and immunotherapeutics made with the ChAdOx1 vector, it is expected that the higher dose level of ChAdOx1-PCAQ (2.5×10^{10} viral particles [vp]; Cohorts 2 and 3) will be more immunogenic and therefore will be chosen over the lower dose if both have acceptable safety. Similarly, for IM administration of MVA-PCAQ, the higher of the 2 IM doses (2×10^8 plaque forming units [pfu] IM; Cohort 2) is expected to be more immunogenic and will be chosen over the lower dose if both have acceptable safety.

Based on previous preclinical and clinical experience with vaccines and immunotherapeutics made with the MVA vector used as a booster, it is expected that the IV route of administration will result in enhanced T cell responses and better delivery of T cells to tissues, resulting in better efficacy. Therefore, the IV route of administration of MVA-PCAQ (Cohort 3) will be chosen over the IM route if both have acceptable safety.

4.1.4 Duration of Trial for Participants

The trial consists of the following periods:

- Screening Period: Up to 42 days from informed consent until VTP-850 prime dose.
- Intervention Period: From VTP-850 prime dose until the Day 91 Clinic Visit.

Short-term Follow-up Period: All participants will be followed monthly from the end of the intervention period until the Month 6 Visit or until start of new therapy such as ADT or development of unequivocal metastatic prostate cancer, if sooner. If a participant does not have a PSA response by their Month 6 visit, they will complete their EoT visit and will not enter the Long-term Follow-up Period.

Long-term Follow-up Period: Participants who have PSA response will be followed for an additional 18 months, up to 24 months from first dose, or until start of new therapy such as ADT or development of unequivocal metastatic prostate cancer, if sooner. Clinic visits will be monthly to Month 12 and bimonthly thereafter. If a participant has a significant decrease in PSA but does not meet the criteria for a PSA responder e.g., the confirmatory measurement is not yet performed, discuss with the Medical Monitor whether the participant should continue follow-up.

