| Immunogenicity assessments | | | | | | | | |
| Blood for PBMC assessment ^f | | | | | X | X | | |
| Blood for anti-antigen antibody assessment | | | | | X | X | | |

Abbreviations: AESIs- Adverse Events of Special Interest, d=days, EOT=End of Trial, PBMC=peripheral blood mononuclear cells, PSA=prostate-specific antigen, PSMA=prostate-specific membrane antigen

^a Participants will only have 1 EOT visit at either Months 6 or 24 or earlier in the event of initiation of new therapy (such as ADT) or development of unequivocal metastatic prostate cancer. Participants with no PSA response in the first 6 months will not enter the Long-Term Follow-up Period. Participants with a PSA response through Month 6 will enter the Long-term Follow-up Period.

^b Visits during the Follow-up Periods are from Day 1. Windows are relative to the target date of the visit.

^c If a cardiac event is reported, blood should be taken for an additional assessment of troponin T and the participant should undergo an additional ECG and echocardiogram at the earliest opportunity

^d If troponin T test result is abnormal, a re-test on the following day is required.

^e PSMA scan can be performed at any time for participants who had a positive PSMA scan prior to screening and where a 50% reduction from baseline in PSA is observed.

^fOnly required at sites qualified by Barinthus Biotherapeutics to perform PBMC isolation/processing.

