2.2 Background

Prostate cancer is the second most frequent cancer diagnosis in men and the fifth leading cause of cancer-related deaths in men worldwide.^[2] In 2018, approximately 1.3 million new cases were diagnosed, and approximately 360,000 deaths occurred. The incidence and mortality of prostate cancer increase with age, with the average age of diagnosis being 66 years.^[2] Furthermore, the incidence of prostate cancer is expected to increase due to longer life expectancy and lifestyle factors. The rates are highest in North America, Australia, and northern and central Europe, and lowest in south-eastern and south-central Asia and northern Africa.^[2]

The serum concentration of PSA is usually elevated in men with prostate cancer and is used to monitor the progression of prostate cancer in men who have already been diagnosed with the disease. About 90% of patients with prostate cancer have localised or regional disease at the time of diagnosis. Localised or regional prostate cancer can be treated with radiation or surgical removal of the prostate. These localised therapies can be curative, but the cancer recurs in approximately 20% to 30% of patients. Patients with localised prostate cancer may also receive androgen deprivation therapies (ADTs), as androgens stimulate the growth of prostate cancer cells. Patients with recurrent disease are typically offered ADT when they present with symptomatic local disease progression, proven metastases or a PSA doubling time of less than 3 months.^[3] If a patient has evidence that their cancer is progressing despite ADT, such as increasing PSA in their blood or new bone metastases, it signifies that their disease is castration-resistant.^[4]

Once prostate cancer becomes metastatic, it is considered incurable. Current treatment options for metastatic prostate cancer include androgen receptor inhibitors, such as enzalutamide and abiraterone; chemotherapy including docetaxel and cabazitaxel; a radioactive isotope radium-223; lutetium vipivotide tetraxetan, a radiopharmaceutical, and sipuleucel-T, a patient-specific immunotherapeutic. All of these treatments have been shown to improve survival, but once the cancer is castration-resistant, the median overall survival is less than 3 years.

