3 OBJECTIVES AND ENDPOINTS

| Primary Objective | Primary Endpoints |
|--|---|
| To evaluate the safety of VTP-850 prime-boost regimens, with the booster dose administered either IM or IV, and establish an RP2R | 
 Number and proportion of participants with AEs, treatment-related AEs, \geGrade 3 AEs, \geGrade 3 treatment-related AEs, serious adverse events, and treatment-related serious adverse events Number and proportion of participants with clinically significant laboratory values Change from baseline for laboratory tests and vital sign measurements at each time point of collection |
| Secondary Objectives | Secondary Endpoints |
| To evaluate the PSA response rate to VTP-850 | 
 Percentage of participants with \ge50% reduction in serum PSA compared to baseline at any time, based on two consecutive measurements, at least 2 weeks apart |
| To evaluate the durable PSA response rate to VTP-850 | 
 Percentage of participants with confirmed PSA response compared to baseline without having PSA progression on or before Month 8. |
| To evaluate the duration of PSA response to VTP-850 (for the subset of participants with PSA response) | 
 Duration of PSA response (for the subset of participants with PSA response), defined as time from date of first dose of VTP-850 to the date of PSA progression (i.e., an increase of \ge25% and an absolute increase of 0.2 ng/mL or more from nadir) |
| To assess the Metastasis-free Survival (MFS) and Time to Metastases (TTM) of the subset of participants with PSA response | 
 MFS is defined as the time from date of first dose of VTP-850 until metastatic disease by conventional imaging (CT/MRI and/or technetium-99 bone scan) or death from any cause, whichever occurs first TTM is defined as the time from date of first dose of VTP-850 until metastatic disease by conventional imaging (CT/MRI and/or technetium-99 bone scan) 
Note that MFS and TTM events do not include local progression events, e.g., progression in pelvic lymph nodes below the aortic bifurcation.
 |
| To assess the time to start of ADT for the participants with PSA response | 
 Time from date of first dose of VTP-850 to the earliest of the start of ADT or the date when criteria to start ADT are met |
| Exploratory Objectives | Exploratory Endpoints |

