11.2.3.4 Metastasis-Free Survival and Time to Metastases

The duration of MFS, defined as the time from first dose of VTP-850 to detection of metastatic disease or all-cause mortality, will be summarised (n, median, interquartile range, minimum, maximum) and presented using a Kaplan-Meier plot. Participants who have survived without development of metastatic disease by the end of follow-up will be censored at the time of their last follow-up visit with an evaluable assessment of metastatic disease.

The duration of TTM, defined as the time from first dose of VTP-850 to detection of metastatic disease, will be summarised (n, median, interquartile range, minimum, maximum) and presented using a Kaplan-Meier plot. Participants who have not developed metastatic disease by the end of follow-up will be censored at the time of their last follow-up visit with an evaluable assessment of metastatic disease.

These endpoints will be further summarised by whether the participants had prior radical prostatectomy, external beam radiation or brachytherapy. These endpoints will be further summarised for participants who experienced a PSA response.

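### MFS and TTM are defined without regard to new therapy, but follow-up stops when new therapy starts, so the censored Kaplan-Meier curves do not estimate the endpoints as defined; the direction of the error is uncertain

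*Protocol*

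**What the plan says.** **Endpoint definitions (Protocol section 3, repeated in the synopsis; MFS also in 8.2.3).** "MFS is defined as the time from date of first dose of VTP-850 until metastatic disease by conventional imaging", with the event completed by "or death from any cause, whichever occurs first". For the second endpoint, "TTM is defined as the time from date of first dose of VTP-850 until metastatic disease by conventional imaging". Neither definition mentions new therapy.

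**Follow-up (Protocol 4.1, 4.1.4 and Table 2; SAP 2.1 and 5.1.3).** Responders are followed "up to 24 months from first dose, or until start of new therapy such as ADT or development of unequivocal metastatic prostate cancer". Footnote a of Table 2 allows a single End of Trial (EOT) visit, which comes "earlier in the event of initiation of new therapy (such as ADT) or development of unequivocal metastatic prostate cancer". No scan is scheduled after it.

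**Analysis (Protocol 11.2.3.4).** Men without an event "by the end of follow-up will be censored at the time of their last follow-up visit with an evaluable assessment of metastatic disease". The section has no separate rule for men who leave because of new therapy.

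**Why ADT starts (Protocol 2.2).** Men with recurrence are typically offered it on "symptomatic local disease progression, proven metastases or a PSA doubling time of less than 3 months". Section 7.2 gives rapid PSA progression as an example of a reason to leave the trial and consider other treatment.

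**SAP.** It covers Phase 1 only and leaves MFS and TTM to a future Phase 2 SAP (2.1, 2.2.2, 2.2.3). Its only strategy for ADT as an intercurrent event, while on treatment, belongs to the safety estimand (3.1.4, Table 3).

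**The concern.** Kaplan-Meier estimation assumes that a man censored today has the same later risk as those still followed. Here men are censored because they start treatment, and the Protocol's own account of when ADT is offered suggests that they are likely to be at higher risk. Metastases and deaths after that point belong to the endpoints as written but cannot enter the curves.

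Protocol 2.1 relies on following responders for metastasis and for new treatment to characterise the quality of PSA responses, and Appendix 6 records that responder TTM was added after regulatory requests. A reader will take the responder curves as MFS and TTM as defined. They describe something else, and nothing in the planned output says so.

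The issue concerns responders through Month 24. The exit of non-responders at Month 6 ("If a participant does not have a PSA response by their Month 6 visit, they will complete their EoT visit") is a separate loss that affects the exploratory curves for all participants.

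**Working it through.** **The plan's own figure.** There is none: the documents give no event rate, event count or precision for MFS or TTM. The 89.3% Phase 2 power in 11.4 concerns PSA response. It reproduces (0.8932 for at least 20 of 125 at a true rate of 20%) and is not affected.

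**Assumed inputs.** Every rate here is an assumption.
- Metastasis or death: m = 0.015 per month.
- ADT start: a = 0.02, 0.04 or 0.06 per month.
- Both are multiplied by one gamma frailty with mean 1 and variance v. At v = 0, prognosis is not shared.
- Hazard ratio h for metastasis or death after ADT.
- Horizon t = 24 months, with censoring at the ADT date.

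**Formulas.** Let L(x) = (1 + vx)^(−1/v), or e^(−x) when v = 0.
- Censored curve: KM = (1 + v(a+m)t)^(−m/(v(a+m))), or e^(−mt) when v = 0.
- MFS as defined: S = L((a+m)t) + [a/(a+m−mh)] × [L(mht) − L((a+m)t)].
- Share of men censored by ADT: [a/(a+m)] × [1 − L((a+m)t)].
- Share of events never counted: 1 − [m/(a+m)] × [1 − L((a+m)t)] / (1 − S).

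**One case in full (v = 1, a = 0.04, h = 0.5).** (a+m)t = 0.055 × 24 = 1.32 and mht = 0.18.
- KM = 2.32^(−0.015/0.055) = 0.795.
- S = 1/2.32 + [0.04/0.0475] × [1/1.18 − 1/2.32] = 0.431 + 0.842 × (0.847 − 0.431) = 0.782.
- The censored curve is 1.3 points too high.

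**Results at a = 0.02, 0.04, 0.06** (differences taken before rounding):

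| v | h | KM | MFS as defined | KM minus defined, points |
|---|---|---|---|---|
| 1 | 1 | 0.770, 0.795, 0.814 | 0.735 | +3.5, +6.0, +7.9 |
| 2 | 1 | 0.810, 0.838, 0.858 | 0.762 | +4.7, +7.6, +9.6 |
| 1 | 0.5 | 0.770, 0.795, 0.814 | 0.765, 0.782, 0.793 | +0.5, +1.3, +2.1 |
| 2 | 0.5 | 0.810, 0.838, 0.858 | 0.790, 0.805, 0.814 | +1.9, +3.4, +4.4 |
| 1 | 0.3 | 0.770, 0.795, 0.814 | 0.779, 0.804, 0.821 | −0.9, −1.0, −0.7 |
| 0 | 1 | 0.698 | 0.698 | 0 |
| 0 | 0.5 | 0.698 | 0.725, 0.746, 0.761 | −2.8, −4.8, −6.3 |

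At v = 1, 26 to 51% of men are censored by ADT. At h = 0.5, 17 to 43% of the events by Month 24 are never counted (v = 1 to 2).

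**Check with the scan schedule.** A separate simulation, 200,000 men per scenario with deaths ignored, used scans every 6 months to Month 24. It assumed a 24-month metastasis risk of 20 or 40%, ADT starts of 30 or 60%, h from 0.3 to 1, and a log-normal shared frailty with SD 0 or 1.
- Shared prognosis and h = 1: +3.5 to +11.3 points without a scan at ADT start, +2.1 to +6.5 with one.
- All scenarios: −11.6 to +11.3 points, with 5 to 64% of metastases never observed.

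**The case against.** **The direction is not fixed.** A reader might infer that the curves must look too good. The documents do not support that. MFS as defined continues through ADT, so any benefit of ADT belongs to the target. Losing that benefit pushes the censored curve down, while selective censoring pushes it up. This objection stands in full.

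**The link to prognosis is partly inference.** A reader might also infer that the men censored are those closest to metastasis. Section 2.2 is general background, not a trial rule. One of its three triggers is proven metastases, and a man whose metastasis is shown on conventional imaging is an event, not a censored case. What remains is that men starting ADT are likely to be at higher risk, which is enough to doubt uninformative censoring.

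**An EOT scan may help.** Table 2 places imaging in the Month 6/EOT and Month 24/EOT columns, so a scan at ADT start may find metastases already present. In the scan-schedule check with shared prognosis and no ADT effect, this shrinks the gap without closing it. It cannot find later metastases.

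**ADT is already reported.** Section 11.2.3.5 gives time to ADT in responders, and 11.2.5.1 gives reasons for withdrawal. These show how often ADT occurs, but not how the MFS and TTM curves should be read.

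**The stakes are modest.** The endpoints are descriptive. At the 20% response rate used in 11.4 there would be about 25 responders among 125 men, and a 95% interval around 0.735 is about ±1.96 × √(0.735 × 0.265/25) = ±17 points. The Phase 2 SAP is still to be written. All true, and the reason for keeping the remedy small.

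**A target before new therapy is defensible.** In a single-arm trial, MFS regardless of ADT mixes the effects of VTP-850 and ADT. This is right, and it argues for stating that target openly.

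**Conclusion.** The mismatch is in the text. The definitions ignore new therapy, follow-up ends at it, and the analysis censors there or at an earlier scan. No intercurrent-event strategy or sensitivity analysis is given for MFS or TTM. The curves therefore do not in general estimate the endpoints as defined, and the censoring is probably informative.

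The size depends on rates that the documents do not give. Under the assumed monthly rates, the 24-month value is about 3.5 to 10 points too high with shared prognosis and no ADT effect, and about 0.5 to 4.5 points too high if ADT halves later risk. It is about 1 point too low or less at frailty variance 1 and hazard ratio 0.3, and about 3 to 6 points too low if prognosis is not shared and ADT halves risk. If prognosis is not shared and ADT has no effect, the bias in this model is zero.

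A reader might go further and ask that MFS regardless of new therapy become the main analysis. That would rest on irregular routine imaging after the trial visits end. Nor does the vital-status collection in 7.3 settle it: that text sits under loss to follow-up and is not tied to MFS or to men who leave for ADT.

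**What to change.** In Protocol 11.2.3.4 and the Phase 2 SAP:

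1. State that the censored MFS and TTM curves describe metastasis-free status while free of new therapy.
2. Report the number of men censored because of new therapy.
3. Add, as a sensitivity analysis, a Kaplan-Meier curve for the first of metastasis, death or start of new prostate cancer therapy. New therapy is then an event, so it no longer censors.

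The cost is one table and one curve. The dates should already be on file: medications including ADT are recorded under 6.10, and procedures are listed under 11.2.5.4. The composite has limits. It also reflects decisions to start therapy, and men who withdraw under 7.2 before starting any remain censored in it.

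Optionally, record vital status and routine-care metastasis dates to Month 24 after new therapy starts. Treat these as supportive data and do not let them replace the main analysis, because routine imaging will be less regular than the trial schedule. No change to sample size or to the PSA-response decision rules is needed.
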